5.7 Sponsor's Qualified Medical Personnel

Contact information for the sponsor's appropriately qualified medical personnel for the study is documented in the Study Contact List located in the investigator study master file held at the study site.

The contact number is only to be used by investigational staff seeking advice on medical questions or problems in the event that the established communication pathways between the investigational site and the study team are not available.

The contact number is not intended for direct use by study subjects. To facilitate access to appropriately qualified medical/dental personnel on study-related medical/dental questions or problems, subjects will be provided with a contact card. The contact card will provide, as a minimum, protocol identifiers, the subject's study identification number, contact information for the investigational site, and contact details in the event that the investigational site cannot be reached to provide advice on a medical question or problem identified by a healthcare professional other than the investigator.

6 INVESTIGATIONAL/STUDY PRODUCTS

For the purposes of this study, per International Conference on Harmonization (ICH) guidelines, and GSK policy, investigational product is defined as a pharmaceutical form of an active ingredient, a non-medicinal product (marketed or investigational), or a placebo, being tested or used as a reference (positive or negative control), in a clinical trial. This includes a product with a marketing authorization when used or assembled (formulated or packaged) in a way different from the approved form, or when used for an unapproved indication, or when used to gain further information about an approved use.

6.1 Investigational/Study Product Supplies

The following study products will be supplied by the Clinical Supplies Department, GSK CH:

Table 6-1	Investigational/Study Product Supplies
-----------	--

	Active Treatment ^a	Active Comparator ^b	Placebo Product for Blinding of Active Treatment ^a
Product Name	DDEA 2.32% Gel	DDEA 1.16% Gel	Placebo gel - 0% diclofenac gel
Pack Design	2 x 50 g tubes	4 x 50 g tubes	2 x 50 g tubes
Dispensing Details	1 kit per subject at Visit 1ª	1 kit per subject at Visit 1 ^b	1 kit per subject at Visit 1ª
Product Master Formulation Code (MFC)	CCI	CC	CCI
Dose/Application	Gel – 5 cm (2 g) on 200 cm ²	Gel – 5 cm (2 g) on 200 cm ²	Gel – 5 cm (2 g) on 200 cm ²
Route of Administration	Topical	Topical	Topical
Usage Instructions	Two times daily (BID) (morning and late afternoon)	Four times daily (QID)	Two times daily (BID) (noon and late evening)
Return Requirements	All used/unused samples to be returned	All used/unused samples to be returned	All used/unused samples to be returned
Storage Requirements	Store below 25°C	Store below 25°C	Store below 25°C

^a The study products for the Active Treatment and Placebo Product for Blinding of Active Treatment will be provided in a single kit containing 4 tubes (2 tubes of each study product)

^b The study product for the Active Comparator will be provided in a single kit containing 4 tubes (4 tubes of Active Comparator product)

Table 6-2 Rescue Medication Inform
--

	Rescue Medication
Product Name	500 mg paracetamol tablets
Pack Type	Pack of tablets
Dispensing Details	Dispense at Visit 1. May re-dispense at Visit 3 if necessary.
Product Formulation Code	Commercial product
Dose	One 500 mg tablet with water per dose. May be repeated after 4 hours. Maximum daily dose 2000 mg.
Route of Administration	Oral
Usage Instructions	As needed for pain
Return Requirements	All used/unused samples to be returned
Storage Requirements	Store sealed.

Table 6-3Sundry Items

Sundry Items to be supplied:

Item Name	Supplied By	Pack Type	Dispensing Details	Return/Disposal Details	
				Used Samples	Unused Samples
Urine pregnancy test	GSK/CRO/Site*	Unit	To be used by site staff at visit 1	Dispose at site	Return
Dosing Card	GSK	Each	Included in treatment kit	Return	Return
Subject Diary	CRO	Each	To be provided to subjects	Return	Return

* CRO = Contract Research Organization

Detailed instructions for the return of study product/study supplies for the accountability checks and subsequent destruction which will be provided by GSK CH during the course of the study in time for study close out visit.

6.1.1 Dosage Form and Packaging:

DDEA 2.32%, DDEA 1.16%, and placebo gels will be supplied to the clinical site as packaged tubes for dispensing by the pharmacy.

The content of the product labels will be in accordance with all applicable regulatory requirements and will be the responsibility of the GSK CH Global Clinical Supplies group. Each study label will contain, but not be limited to, protocol number, directions for use and storage requirements.

Care should be taken with the supplied products and their labels so that they are maintained in good condition. It is important that all labels remain intact and legible for the duration of the study. Subjects should be instructed to not remove or deface any part of the study label.

All products supplied are for use only in this clinical study and should not be used for any other purpose. Subjects must not exchange their designated products with other study subjects.

6.1.2 Preparation and Dispensing

DDEA 2.32% gel, DDEA 1.16% gel, and placebo will be prepared and/or dispensed by qualified site personnel according to the dosage and administration instruction.

Once the eligibility of a subject has been confirmed, the Investigator (or nominated assistant) should contact the IVRS/IWRS Centralized Randomization Centre for allocation of randomized therapy.

The actual treatment given to individual subjects will be determined by a randomization scheme that has been loaded into the (IVRS/IWRS) database. Subjects will be assigned to products in accordance with the randomization schedule generated by an approved GSK CH vendor, using validated software.

All subjects will be identified to the Centralized Randomization Centre using an Interactive Response Technology (IRT). Before the study is initiated, training, login information and directions for the IRT will be provided to each site.

The IVRS/IWRS Centralized Randomization Centre will inform the investigator of the Kit ID number to be allocated to the subject after subjects become eligible for randomization.

6.2 Administration

All subjects will be given 4 tubes of study drug and the same usage instructions. Subjects should spread a total of approximately 2 grams of study medication (using the dosing card) on both sides of the ankle. The study drug should be applied topically with the fingertips to both sides of the affected ankle for approximately 1 minute (corresponds to a region of approximately 200 cm²). After application, the hands should be washed. On Day 1, to demonstrate proper application, the first dose of study drug will be applied at the study center from the morning tube (regardless of the time of randomization). Subsequent doses will be applied from the tube associated with the corresponding time of day separated by at least 3 hours (i.e. if the first dose is applied at 15:00 hr from the morning tube, the next dose will be at approximately 18:00 hr from the late afternoon tube and the next dose will be applied on Day 1, if possible, preferably with at least 3 hours between doses.

The subjects will be instructed to continue to apply the gel topically with the fingertips four times a day for 7 days. Dosing times should be distributed as evenly as possible over the day, preferably once upon first arising (i.e., after washing or shower or bath), once at lunch (approximately 12:00 hour), once in the late afternoon (approximately 17:00 hour), and once in the late evening (i.e., after washing approximately 21:00 hour). There should be a period of at least 4 hours between individual applications. The appropriately-labeled tube should be used for each application.

Subjects can take a shower or bathe prior to application. Subjects should not shower, bathe or wash the treated area within the first three hours after the application. Subjects should wash their hands after use and should wait 10 minutes before covering the treated skin with clothing.

The investigator will instruct the subject to take the study drug exactly as prescribed and state that compliance is necessary for the subject's safety and the validity of the study. The subject will be told to contact the investigator if he/she is unable for any reason to take the gel as directed/prescribed. All dosages prescribed and dispensed to the subject and all dose changes during the study must be recorded on the Dosage Administration Record CRF. Any missed or skipped doses must be recorded in CRF.

Subjects will be instructed to self-administer their assigned product per the above usage instructions which will be explained and provided to the subject.

6.2.1 Medication/Dosing Errors

Medication/dosing errors may result, in this study, from the administration or consumption of:

- the wrong product,
- by the wrong subject,
- at the wrong time,
- or at the wrong dosage.

Such medication/dosing errors occurring to a study subject are to be captured in the CRF. In the event of medication dosing error, the sponsor should be notified immediately.

Medication/dosing errors are reportable irrespective of the presence of an associated AE, including:

- Medication/dosing errors involving subject exposure to any of the study products;
- Potential medication/dosing errors or uses outside of what is foreseen in the protocol that do or do not involve the participating subject.

If a medication/dosing error is accompanied by an AE, as determined by the investigator, the medication/dosing error and, any associated adverse event(s) are to be captured in the CRF AE form.

6.3 Investigational/Study Product Storage

The investigator, or designee, will ensure that all study products are stored in a secured area with controlled access under required storage conditions and in accordance with applicable regulatory requirements and the product label.

Site systems must be capable of measuring and documenting (for example, via a log), at a minimum, daily minimum and maximum temperatures for all site storage locations (as applicable, including frozen, refrigerated, and/or room-temperature products). This should be captured from the time of first product receipt throughout the study. Even for continuous monitoring systems, a log or site procedure that ensures active daily evaluation for excursions should be available. The operation of the temperature-monitoring device and storage unit (for example, refrigerator), as applicable, should be regularly inspected to ensure it is maintained in working order.

Any excursions from the product-label storage conditions should be reported to appropriate site staff upon discovery and communicated to sponsor as soon as possible. The site should actively pursue options for returning the product to the storage conditions as described in the labeling, as soon as possible. Excursions from the storage requirements, including any actions taken, must be documented as a protocol deviation and reported to the Sponsor.

Once an excursion is identified, the affected product (or products) must be quarantined and not used until the sponsor provides documentation of permission to use. Use of any of the affected product(s) prior to sponsor approval will be considered a protocol deviation.

Site staff will instruct subjects on the proper storage requirements for all take-home products.

6.4 Investigational/Study Product Accountability

All products supplied are for use only in this clinical study and should not be used for any other purpose.

All study products must be received by a designated person at the study sites, handled and stored safely and properly, and kept in a secured location to which only the study staff have access. Upon receipt, all study products should be stored according to the instructions specified on the product labels (Table 6-1,Table 6-2). Study products are to be dispensed only to subjects enrolled in the study in accordance with the protocol, by authorized site staff.

The investigative site must maintain adequate records documenting the receipt, use, loss, or other disposition of all the product supplies. All study products will be accounted for using the investigational/study product accountability form/record. The investigator is responsible for study product accountability, reconciliation, and record maintenance.

The accountability records must be available for inspection by the study monitor during the study. Monitoring of product accountability will be performed by the monitor during site visits and at the completion of the study.

All unused product must be returned at the final Visit 4. The monitoring plan will describe the process for investigational product accountability.

The inventory must be available for inspection by the study monitor during the study.

6.4.1 Destruction of Investigational/Study Product Supplies

At the conclusion of the study, the Principal Investigator or an appropriate designee, and a representative of GSK CH (study monitor) will inventory all used and unused study products and sundry items. The investigational/study product accountability record for returned study products will then be completed. All study product (used and unused) for this clinical study (including emptying containers) will be returned for destruction to the GSK CH Clinical Supplies Department or designated vendor using the return instructions provided.

6.5 Blinding and Allocation/Randomization

At Visit 1, participants who fulfill all the inclusion criteria and none of the exclusion criteria will be assigned a unique randomization number in ascending numerical order at each study site. The randomization number encodes the participant's assignment to one of the two arms of the study according to the randomization schedule generated prior to the study. These randomization numbers are linked to the two treatment arms, which in turn are linked to container (kit) numbers. A separate container list will be produced. Subjects will be randomized

GlaxoSmithKline Consumer Healthcare Confidential Template Version Effective: 18-May-18 (CCR #11475) Page **29** of **64**

Diclofenac Diethylamine 2.32% Study 211206 Protocol Amendment 1

using an interactive response technology system and container numbers will be provided by the system.

Subjects will be randomized in a 1:1 ratio, with equal numbers receiving DDEA 2.32% + Placebo gel and DDEA 1.16% gel. Randomization numbers will be assigned to individual centers in order to stratify the randomization by center.

Before the study is initiated, training, login information and directions for the IRT will be provided to each site. Study products will be dispensed according to the instruction received through the IRT at the appropriate study visits.

Returned study products should not be re-dispensed to any subject.

The investigator's knowledge of the product allocation should not influence the decision to enroll a particular subject or affect the order in which subjects are enrolled.

This study is described as double-blind (the subjects and clinical examiner will be blinded to the product received). The study statistician, data management staff, other employees of the Sponsor and vendors acting on behalf of the sponsor, who may influence study outcomes will also be blinded to the product allocation. The placebo gel and active gels will be identical in packaging, labeling, odor, schedule of administration, and as identical as possible in appearance.

To ensure the examiner remains blinded throughout the study, staff involved in the preparation, dispensing, and application of study products will work in a separate area. The examiner is not permitted in any area where study product is stored, dispensed, or in use.

Subjects will be instructed not to remove study products from the opaque bags provided outside of the dispensing room, while at the study site. Dispensing staff and staff supervising administration of IP will not be involved in any efficacy/safety assessment procedures during the study.

Randomization data will be kept strictly confidential, accessible only to authorized persons, until the time of unblinding. After the study is completed, the data file verified, and protocol violations determined, drug codes will be broken and made available for data analysis.

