12.2.2 Exclusion of Data from Analysis

Exclusion of any data from the analyses will be determined during a Blind Data Review Meeting prior to database lock. Any reasons for exclusion from an analysis population will be listed, if applicable.

Protocol deviations that would exclude subjects from the PP population may include (but are not limited to) the following:

- Subjects failing to meet inclusion and exclusion criteria but were included in the study.
- Subjects without a Day 5 pain on movement VAS assessment
- Subjects with poor or moderate compliance with study treatment
- Subjects taking prohibited medication
- Subjects identified with other major protocol deviations

Further detail is provided in the statistical analysis plan.

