## 2.2 Final Analyses

The final planned analyses will be performed after the completion of the following sequential steps:

- 1. All subjects have completed the study as defined in the protocol
- 2. Finalization and signature the RAP.
- 3. All required database cleaning activities have been completed and database has been locked.
- 4. All criteria for unblinding the randomization codes have been met and the randomization codes have been distributed.

GlaxoSmithKline Consumer Healthcare Confidential Page 9 of 36

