## 4 Data Analysis

Data analysis will be performed by Biostatistics and Programming Team at IQVIA Biotech Pvt. Ltd. The statistical analysis software used will be SAS version 9.4 or higher in a WINDOWS environment.

Prior to database closure a Blind Data Review Meeting (BDRM) will be conducted in which various aspects of the trial will be discussed and agreed.

Except as described below, all listings will be produced for Enrolled and/ or Intent To Treat (ITT) subjects.

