  - Over all Compliance % = [sum of (actual # of application from each tube)/sum of (expected # of application from each tube)\*100]

Scheduled applications will include all scheduled applications through the day before the final visit. On day 1, the percentage of gel used will be calculated based on the possible number of administrations on that day. If only 3 were possible, then 100 % compliance on that day will be considered 3 applications.

- % of gel used relative to number of actual applications \* 2g will be derived as following -
  - Total weight of study medication used: The percent (%) of gel used will be computed relative to the actual number of application made from randomization through the final visit multiplied by 2 g.in two ways –
  - If replacement kit number and replacement date (CRF: Study Medication Replacement) are missing then
  - Expected weight of study medication used from tube k= (number of applications per day from tube k )\*2g \* Expected number of days gel to be applied from tube k
  - Actual weight of study medication used from tube k= [(Baseline weight of tube k (weight of tube k after last day of application ; k=1, 2, 3, 4

GlaxoSmithKline Consumer Healthcare Confidential Page 16 of 36

**Percent of total medication used** = (Actual weight of medication used/Expected weight of medication used)\*100

In case there is repeated usage of single tube in a day then the over usage of the medication will be reflected in weight compliance.

- Compliance category: Compliance category will be defined in the following way -
  - Good: > 80% of the gel has been applied and > 80% of scheduled applications made,
  - Moderate: not Good and not Poor
  - Poor: < 50% of the gel has been applied or < 50% of scheduled applications made.

For subjects applying active gel only twice per day (DDEA 2.32%), an additional compliance computation will be performed relative to the tubes and applications of active gel. If a subject is falls into good compliance category in both (separately for the active gel and also combined with placebo) then that subject will be included in the PP protocol population.

For each subjects time of the first application, application of the study drug each time point each day and the weight of the four tubes on Day 1, 3, 5 and 8 will be listed in **PPD** :

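### A PP-inclusion sentence in SAP 4.4.1 covers only DDEA 2.32% subjects, conflicts with the common cut-offs in SAP 4.2.2 and 4.2.3, and cannot be finally applied without the treatment code

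*Protocol*

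**What the plan says.** **Timing and blinding.** Protocol 6.5 fixes the order: "After the study is completed, the data file verified, and protocol violations determined, drug codes will be broken and made available for data analysis". It keeps blind "The study statistician, data management staff, other employees of the Sponsor and vendors acting on behalf of the sponsor, who may influence study outcomes". Protocol 12.2.2 adds: "Exclusion of any data from the analyses will be determined during a Blind Data Review Meeting prior to database lock". SAP 4 plans the same meeting before database closure, and SAP 4.2.3 sends PP exclusions to it. In SAP 2.2 the last step, after lock, is "All criteria for unblinding the randomization codes have been met and the randomization codes have been distributed".

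**Common PP rule.** SAP 4.2.2 lists as PP exclusions application compliance of 80% or less, weight compliance of 65% or less, and either measure at 143% or more. SAP 4.2.3 repeats the lower limits. Neither section mentions an arm.

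**Arm-specific sentence.** SAP 4.4.1 defines Good as more than 80% of gel and more than 80% of scheduled applications. It continues: "For subjects applying active gel only twice per day (DDEA 2.32%), an additional compliance computation will be performed", using the active-gel tubes. A subject who is Good "in both (separately for the active gel and also combined with placebo) then that subject will be included in the PP protocol population". Protocol 12.2.4.1 has the same additional computation but does not link it to PP.

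**Role of PP.** SAP 4.5.1.2 makes PP without imputation the primary non-inferiority analysis. SAP 5 records that the PP definition and the compliance criterion were changed, but does not mention the PP sentence in 4.4.1.

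**The concern.** Only the DDEA 2.32% arm receives placebo gel, so the check on active gel separately and combined with placebo has meaning in that arm alone. Two subjects with identical tube records can then have different PP status because of their allocation. That is asymmetric selection into the set on which non-inferiority is declared. It also means that the final status of some subjects cannot be fixed at a blind meeting, which is where the protocol and the rest of the SAP place that decision.

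The sentence also disagrees with 4.2.2 and 4.2.3 on the cut-offs themselves: more than 80% of gel for Good, against more than 65% for PP, and no upper limit against 143%. Nothing states which text prevails.

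**Working it through.** **1. The plan's own sample size.** Inputs from Protocol 12.1: margin 13 mm, SD 22 mm, true difference 5 mm in favor of DDEA 1.16%, two-sided 95% CI, 80% power.

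n per arm = 2 × (1.960 + 0.842)² × 22² / (13 − 5)² = 118.7, so 119, against about 120 stated. Power at 120 per arm is 80.4%. The figure reproduces.

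**2. The 4.4.1 sentence as a requirement.** Protocol Table 6-1 gives the test arm's active gel as morning and late afternoon. Take 7 full days: 28 scheduled applications, 14 of them from those two tubes. Let all misses fall on those tubes.

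| Misses | Active tubes | All tubes | 4.2.2/4.2.3 applications (>80%) | Good on active tubes |
|---|---|---|---|---|
| 2 | 12/14 = 85.7% | 26/28 = 92.9% | pass | pass |
| 3 | 11/14 = 78.6% | 25/28 = 89.3% | pass | fail |
| 4 | 10/14 = 71.4% | 24/28 = 85.7% | pass | fail |
| 5 | 9/14 = 64.3% | 23/28 = 82.1% | pass | fail |
| 6 | 8/14 = 57.1% | 22/28 = 78.6% | fail | fail |

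With 3 to 5 such misses, and weight within limits, the subject is out of PP on DDEA 2.32% and in PP on DDEA 1.16%.

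Weight gives a second route. With applications above 80% and overall weight compliance above 65% and up to 80%, the subject meets 4.2.2 and 4.2.3 but is not Good on all tubes. The record stays in PP in the comparator arm and is removed in the test arm.

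**3. How many subjects.** SAP 5 says most subjects had weight compliance of 50% to 80%. Those at 65% or below fail in both arms; those above 65% have a status that depends on allocation. The split is not given, so the group cannot be counted.

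For the application route alone, an illustration with assumed independent miss rates of 5%, 8% and 10%:

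- Test arm, P(at least 3 of 14 active or at least 6 of 28 missed) = 3.1%, 10.2%, 17.3%.
- Comparator, P(at least 6 of 28 missed) = 0.2%, 2.1%, 5.5%.
- Difference × 150 = about 4, 12 and 18 subjects. With the clinic-applied first dose counted as taken: about 3.5, 10 and 15.

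**4. Effect on power, as an assumption only.** If 0%, 5%, 10% or 20% of 120 test-arm subjects are removed and the comparator stays at 120, SE = 22 × √(1/120 + 1/n) with n = 120, 114, 108 or 96. Power = Φ(8/SE − 1.960) = 80.4%, 79.4%, 78.3% or 75.7%. The loss of precision is modest; the main issue is who is selected.

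**5. The sentence as a sufficient condition.** A subject Good on all tubes already exceeds the lower limits in 4.2.3, so the sentence removes nobody. But Good has no ceiling. A DDEA 2.32% subject who is Good on both counts with 150% weight compliance is included under 4.4.1 and listed for exclusion under 4.2.2. A DDEA 1.16% subject with the same record has no such inclusion.

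**6. What can be done blind.** Protocol 6.7 records applications separately for each time-labelled tube and weighs the tubes, for every subject. Both compliance figures can therefore be computed for everyone without the code. Only the step that decides to whom the sentence applies needs it.

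**The case against.** The strongest case against is that the sentence is a remnant. SAP 5 explains that the PP definition was revisited because most subjects fell at 50% to 80% on weight. Requiring more than 80% in the test arm would largely undo that change there, so 4.2.2 and 4.2.3 look like the operative rules, and they can be run blind. Taken literally, the sentence also only says who is included. And the primary endpoint is analyzed on mITT, and on ITT with multiple imputation, neither of which depends on it.

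Much of this stands. The remnant reading is plausible, and the mITT and ITT analyses are real safeguards. But no text retires the sentence or gives 4.2.2 and 4.2.3 precedence, the literal reading still treats the arms differently at 143%, and PP remains the SAP's primary set.

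A reader might go further and infer that the compliance check cannot be run blind at all, or that the sponsor plans to set test-arm flags after unblinding. The documents support neither. The active tubes are fixed by time of day and tube data exist for all subjects, so only the arm look-up needs the code. Every passage on exclusions points to blind review.

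**Conclusion.** The SAP holds two PP compliance rules that disagree, and one of them is tied to an arm. On either reading of 4.4.1, membership of the primary set can depend on allocation, and its final application needs the code, contrary to Protocol 6.5 and 12.2.2.

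The size is undetermined. As a requirement, the rule affects test-arm subjects with overall weight compliance above 65% and up to 80%, and those with 3 to 5 misses concentrated on the active tubes (28 scheduled doses assumed). The SAP 5 remark suggests that the first group could be large. The 4, 12 or 18 removals per 150 rest on assumed, independent miss rates and cover the application route only; they are not estimates for this trial. As a sufficient condition, the rule affects only test-arm subjects at 143% or more.

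It is tempting to conclude that the result would be biased towards non-inferiority, because a more adherent test arm would remain. That direction is plausible under the requirement reading, but the documents do not establish or quantify it. The point rests on the loss of blind, symmetric selection.

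**What to change.** Delete the PP sentence from SAP 4.4.1, or remove its arm label and bring it into line with 4.2.2 and 4.2.3. PP compliance is then governed only by the common cut-offs, applied identically to all subjects on all four tubes. Freeze the flags at the Blind Data Review Meeting before the codes are released, and record the change in SAP 5.

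Keep the active-gel computation as a descriptive summary for DDEA 2.32% after unblinding. Before it is programmed, reconcile the placebo times: SAP 1.3 lists morning and late afternoon, Protocol Table 6-1 lists noon and late evening.

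There is no need to judge DDEA 1.16% subjects on the morning and late-afternoon tubes alone, since those hold only half of their active doses.

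The cost is SAP wording, with no new data. The downside is that test-arm subjects with low active-gel compliance but acceptable overall compliance stay in PP. A sensitivity analysis can examine them.
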